7.2.7. Pharmacokinetic Analysis

Population pharmacokinetic analysis will be performed to describe the plasma concentration profiles of lumasiran. The impact of relevant patient covariates such as age, weight, race, gender, hepatic impairment, and renal impairment on the PK of lumasiran will be assessed using population PK approach.

For patients enrolled in East Asian centers with 24-hour PK collection, pharmacokinetic analyses of plasma and urine will be conducted using noncompartmental methods. Plasma pharmacokinetic parameters including, but will not be limited to: maximum plasma concentration (C_{max}), time to maximum plasma concentration (t_{max}), elimination half-life ($t_{1/2\beta}$), area under the concentration-time curve (AUC), apparent clearance (CL/F), and apparent volume of distribution (V/F) will be determine using noncompartmental approach. Other parameters may be calculated, if deemed necessary. In addition, relevant urine PK parameters will be calculated using 24-hour urine PK profiles.

7.2.8. Safety Analyses

The primary parameter is the frequency and seriousness of AEs. Safety parameters also include vital signs, ECGs, clinical laboratory assessments and physical exams. The extent of exposure will also be summarized. The primary summaries of the safety of lumasiran versus placebo will be based on safety parameters within the 6-month double-blind treatment period, using the Safety Analysis Set. Additional safety analyses will also be performed for the extension periods.

Prior and concomitant medications will be coded using the World Health Organization (WHO) Drug Dictionary. Results will be tabulated by Anatomical Therapeutic Chemical (ATC) Classification System and Preferred Term (PT).

Adverse events will be coded by the Medical Dictionary for Regulatory Activities (MedDRA). AEs, SAEs, related AEs, and AEs leading to discontinuation will be summarized by System Organ Class (SOC) and PT for each treatment arm. By-patient listings will be provided for deaths, SAEs, and events leading to discontinuation of treatment.

Descriptive statistics will be provided for clinical laboratory data, ECG, and vital signs data. Laboratory shift tables from baseline to worst values will be presented.

Other safety summaries will be presented as appropriate. Further details will be specified in the SAP.

7.2.9. Immunogenicity Analyses

ADA results will be summarized descriptively.

7.2.10. Other Analyses

Other exploratory analyses will be detailed in the SAP.

7.2.11. Interim Analysis

No interim analysis is planned.

7.2.12. Optional Additional Research

Optional additional research may be conducted in the future on the biological samples and/or data collected during the study in accordance with the strict terms of the informed consent form (see Section 4.3.2).

8. STUDY ADMINISTRATION

8.1. Ethical and Regulatory Considerations

This study will be conducted in accordance with the protocol, all applicable regulatory requirements, and the current guidelines of Good Clinical Practice (GCP). Compliance with GCP provides public assurance that the rights, safety, and well-being of study patients are protected consistent with the principles that have their origin in the Declaration of Helsinki.

8.1.1. Informed Consent

The Investigator will ensure that the patient/legal guardian is given full and adequate oral and written information about the nature, purpose, possible risk and benefit of the study.

Patients/legal guardians must also be notified that they are free to discontinue from the study at any time. The patient/legal guardian should be given the opportunity to ask questions and allowed time to consider the information provided. In the case of patients under the age of legal consent, legal guardian(s) must provide informed consent and the patient should provide assent per local regulations and institutional standards.

The patient's/legal guardian's signed and dated informed consent (or assent, if applicable) must be obtained before conducting any study tests or procedures that are not part of routine care. When a patient under the age of legal consent who has been enrolled in the study reaches the legal age of consent, the investigator must obtain the patient's informed consent prior to performing any further research interventions and/or procedures involving that patient.

The Investigator must maintain the original, signed ICF (assent form, if applicable). A copy of the signed ICF (assent form, if applicable) must be given to the patient/legal guardian. The Investigator will inform the patient/legal guardian if new information becomes available that may be relevant to the patient's/legal guardian's willingness to continue participation in the study. Communication of this information should be documented.

8.1.2. Ethical Review

The study protocol, including the ICF (and assent form, if applicable), must be approved or given a favorable opinion in writing by an IRB or IEC, as appropriate. The Investigator must submit written approval before he or she can enroll any patient into the study.

The Investigator is responsible for informing the IRB or IEC of any amendment to the protocol in accordance with local requirements. In addition, the IRB or IEC must approve all patient materials for the study (except those that support the need to remove an apparent immediate hazard to the patient). The protocol must be reapproved by the IRB or IEC upon receipt of amendments and annually, as local regulations require.

Initial IRB approval of the protocol, and all materials approved by the IRB for this study including the patient consent form and assent form, as applicable per institutional standards and recruitment materials must be maintained by the Investigator and made available for inspection.

The Investigator will submit reports of SAEs as outlined in Section 6.5.6.4. In addition, the Investigator agrees to submit progress reports to the IRB or IEC per their local reporting requirements, or at least annually and at the conclusion of the study. The reports will be made available to the Sponsor or designee.

Any communications from regulatory agencies, IRBs, or IECs in regard to inspections, other studies that impact this protocol or the qualifications of study personnel should be promptly reported to the Sponsor or its designee.

The Investigator is also responsible for providing the IRB with reports of any reportable serious adverse drug reactions from any other study conducted with the study drug. The Sponsor or designee will provide this information to the Investigator.

Major changes in this research activity, except those to remove an apparent immediate hazard to the patient, must be reviewed and approved by the Sponsor and the IRB or IEC that approved the study. Amendments to the protocol must be submitted in writing to the Investigator's IRB or IEC and the Regulatory Authority for approval before patients are randomized under the amended protocol, and patients/legal guardian must be re-consented to the most current version of the ICF (and assent form, as applicable).

8.1.3. Serious Breach of Protocol

Investigators must notify the medical monitor within 24 hours of becoming aware of a serious breach of the protocol. A serious breach is a breach that is likely to affect to a significant degree the safety and rights of a study participant, or the reliability and robustness of the data generated in the clinical trial.

8.1.4. Study Documentation, Confidentiality, and Records Retention

All documentation relating to the study should be retained for 2 years after the last approval in an ICH territory or as locally required, whichever is longer. If it becomes necessary for the Sponsor, the Sponsor's designee, applicable IRB/IEC, or applicable regulatory authorities to review or audit any documentation relating to the study, the Investigator must permit direct access to all source documents/data. Records will not be destroyed without informing the Sponsor in writing and giving the Sponsor the opportunity to store the records for a longer period of time at the Sponsor's expense.

The Investigator must ensure that the patients' confidentiality will be maintained. On the eCRFs or other documents submitted to the Sponsor or designees, patients should not be identified by their names, but by the assigned patient number or code. If patient names are included on copies of documents submitted to the Sponsor or designees, the names will be obliterated and the assigned patient number added to the document. Documents not for submission to the Sponsor (eg, signed ICFs) should be maintained by the Investigator in strict confidence.

The Investigator must treat all of the information related to the study and the compiled data as confidential, whose use is for the purpose of conducting the study. The Sponsor must approve any transfer of information not directly involved in the study.

To comply with local and/or regional regulations, this clinical study may be registered and study results may be posted on public registries, such as ClinicalTrials.gov.

8.1.5. End of Study

The end of study is defined as the last patient last visit.

8.1.6. Termination of the Clinical Study or Site Closure

The Sponsor, or designee, reserves the right to terminate the study or a clinical study site at any time. Conditions that may warrant this action may include, but are not limited to:

- The discovery of an unexpected, serious, or unacceptable risk to patients participating in the study

- Failure of the Investigator to comply with the protocol, the requirements of the IRB/IEC or local health authorities, the Sponsor's procedures, or GCP guidelines
- Inadequate recruitment of participants by the Investigator
- The decision on the part of the Sponsor to suspend or discontinue treatment with the study drug

Should the study be terminated, and/or the site closed for whatever reason, all documentation and study drug pertaining to the study must be returned to the Sponsor or its representative, and the Investigators, IEC/IRB and Regulatory Authorities will be promptly informed of the termination and the reason for the decision. The Investigator should promptly inform the patients and assure appropriate therapy and follow-up.

8.2. Data Quality Control and Quality Assurance

8.2.1. Data Handling

Study data must be recorded on CRFs (paper and/or electronic) provided by the Sponsor or designee on behalf of the Sponsor. Case report forms must be completed only by persons designated by the Investigator. If eCRFs are used, study data must be entered by trained site personnel with access to a valid and secure eCRF system. All data entered into the eCRF must also be available in the source documents. Corrections on paper CRFs must be made so as to not obliterate the original data and must be initialed and dated by the person who made the correction.

8.2.2. Study Monitoring

The Monitor, as a representative of the Sponsor, has an obligation to closely follow the study conduct at the site. The monitor will visit the Investigator and clinical study center periodically and will maintain frequent telephone and written contact. The monitor will maintain current personal knowledge of the study through observation, review of study records and source documentation, and discussion of the conduct of the study with the Investigator and staff.

The monitor will review source documents, systems and CRFs to ensure overall quality and completeness of the data and to confirm study procedures are complied with the requirements in the study protocol accurately. The Sponsor, or its designee, will be allowed to conduct site visits to the investigation facilities for the purpose of monitoring any aspect of the study. The Investigator agrees to allow the monitor to inspect the drug storage area, study drug stocks, drug accountability records, patient charts and study source documents, site standard operating procedures and training records, and other records relative to study conduct.

8.2.3. Audits and Inspections

Periodically, the Sponsor or its authorized representatives audit clinical investigative sites as an independent review of core trial processes and documents to determine whether these activities were conducted, and data were recorded, analyzed, and accurately reported according to the protocol, GCP guidelines of the ICH, and any applicable regulatory requirements. A regulatory authority, an IEC or an IRB may visit the site to perform audits or inspections, including source

data verification. The Investigator should contact the Sponsor, or its designee, immediately if contacted by a regulatory agency, an IEC or an IRB about an inspection.

8.3. Publication Policy

It is intended that after completion of the study, the data are to be submitted for publication in a scientific journal and/or for reporting at a scientific meeting. A copy of any proposed publication (eg, manuscript, abstracts, oral/slide presentations, book chapters) based on this study, must be provided and confirmed received at the Sponsor at least 30 days before its submission. The Clinical Trial Agreement among the institution, Investigator, and Alnylam will detail the procedures for Alnylam's review of publications.

Authorship of any publications resulting from this study will be determined on the basis of the Uniform Requirement for Manuscripts Submitted to Biomedical Journals (International Committee of Medical Journal Editors).

10. APPENDICES

10.1. Formulae for Estimated Glomerular Filtration Rate Calculation

Estimated glomerular filtration rate (eGFR; in mL/min/1.73m²) will be calculated from serum creatinine (SCr) based on the Modification of Diet in Renal Disease formula for patients ≥ 18 years of age and the Schwartz Bedside Formula for patients < 18 years of age.

Modification of Diet in Renal Disease Formula [Levey 2009]

- Conventional units
 - $eGFR \text{ (mL/min/1.73m}^2\text{)} = 175 \times (SCr \text{ [mg/dL]})^{-1.154} \times (\text{age})^{-0.203} \times (0.742, \text{ if female}), \text{ or } \times (1.212, \text{ if African American})$
- SI units
 - $eGFR \text{ (mL/min/1.73m}^2\text{)} = 175 \times (SCr \text{ [\mu mol/L]}/88.4)^{-1.154} \times (\text{age})^{-0.203} \times (0.742, \text{ if female}), \text{ or } \times (1.212, \text{ if African American})$

Schwartz Bedside Formula [Schwartz 2009]

- Conventional units
 - $eGFR \text{ (mL/min/1.73 m}^2\text{)} = (0.413 \times \text{height [cm]})/SCr \text{ (mg/dL)}$
- SI units
 - $eGFR \text{ (mL/min/1.73 m}^2\text{)} = (36.2 \times \text{height [cm]})/SCr \text{ (\mu mol/L)}$

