6.3.2. Estimated Glomerular Filtration Rate

Blood samples for the assessment of eGFR will be obtained at the time points specified in the Schedules of Assessment ([Table 1](#) and [Table 2](#)). eGFR (mL/min/1.73m²) will be calculated to assess renal function during the study. The calculation will be based on the Modification of Diet in Renal Disease (MDRD) formula for patients ≥ 18 years of age and the Schwartz Bedside Formula for patients < 18 years of age at screening (Appendix [10.1](#)).[[Levey 2009](#); [Schwartz 2009](#)]

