# 7.3. Subgroup Analysis

Subgroup analyses will be conducted to assess the consistency of the treatment effect during the double-blind period for the primary endpoint within the following subgroups:

- Age (6-11, 12 to 17 vs. ≥18 years at screening)
- Gender (Male vs. Female)
- Race (White vs. Non-White)
- Baseline 24-hour urinary oxalate corrected for BSA (≤1.70 mmol/24h/1.73m^2 vs. (>1.70 mmol/24h/1.73m^2)

- Baseline eGFR ( $\leq 60 \text{ vs.} > 60$ )
- History of renal stones (Yes vs. No)
- Baseline vitamin B6 use (Yes vs. No)
- Region 1 (North America [including US and Canada] vs. Other (outside of North America)).
- Region 2 (Europe vs. Other (outside of Europe))

Other subgroups may be examined, if deemed appropriate.

Subgroup analyses will be performed for the primary endpoint of percent change in 24-hour urinary oxalate corrected for BSA to Month 6 using the FAS population. A forest plot will be generated to illustrate the estimated treatment effect along with the associated 95% confidence interval. If the number of patients in a subgroup for either arm is less than 5 patients, then only descriptive statistics will be generated.

The subgroup analyses may be performed for secondary endpoints.

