### 7.7.2. Clinical Laboratory Data

Clinical laboratory parameters will be expressed in Standard International (SI) units. Laboratory data collected and recorded below lower limit of quantification (LLQ) will be set to the lower limit of detection for calculation of summary statistics. Summaries will only include data from central laboratory. eGFR will not be reported in this section, as this is summarized in the efficacy section. For any local collections of LFTs, these will be included in a separate data listing. Key laboratory parameters will be graded according to NCI CTCAE v5.0.

Summaries for each lab parameter (hematology, chemistry, liver function tests, coagulation and urinalysis), which are continuous variables, will have a tabular summary of descriptive statistics at each scheduled visit. Descriptive statistics include actual value, change from baseline and percent change from baseline at each scheduled visit.

Shift tables will be generated to summarize shifts from baseline categories to the worst post-baseline categories with directionality specified for any labs which could be reported in either direction (e.g. above ULN or below ULN).

Clinical laboratory tests with normal ranges will be classified as Low, Normal, and High. For these tests, abnormal values will be flagged in the listings with H when the value is higher than the upper limit of the reference ranges and with L when the value is lower than the lower limit of the reference ranges.

For hematology and chemistry labs, summary tables of potentially clinically significant abnormalities will also be provided.

All laboratory data will be presented in data listings. Separate listings will be included for those laboratory data collected from local labs such as LFTs. Out of range laboratory results will be identified in listings.

**Liver Function Tests (LFTs):** A listing will be generated for all patients with abnormal liver function tests as defined by ALT>3xULN, AST>3xULN and total bilirubin >2x ULN at any visit.

A tabular summary for LFTs will be generated to summarize the number and associated percentage of patient in each of the categories at any post-baseline visit:

- ALT>1 & ≤3, ALT>3 & ≤5, ALT>5 & ≤10, ALT>10 & ≤20, ALT>20xULN
- AST>1 & <3, AST>3&<5, AST>5& <10, AST>10 & <20, AST>20xULN
- ALT or AST>1 & ≤3, ALT or AST>3 & ≤5, ALT or AST>5 & ≤10, ALT or AST>10 & ≤20, AST or ALT>20xULN
- WNL, ALP>1.5xULN

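### Appendix 10.1 does not define one eGFR value for every patient: the adult sex and race factors are joined by *or*, and the two paediatric unit versions differ by 0.85% (minor)

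*Protocol*

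**What the plan says.** Protocol Appendix 10.1 gives two formulas, each in conventional and SI units. Exclusion criterion 4 (Protocol 4.2) and Protocol 6.3.2 both send the reader there.

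- **Adults (MDRD).** The core is "175 \times (SCr \text{ [mg/dL]})^{-1.154} \times (\text{age})^{-0.203", and the SI version rescales creatinine through "SCr \text{ [\mu mol/L]}/88.4)^{-1.154". In both versions the sex and race factors follow as "0.742, \text{ if female}), \text{ or } \times (1.212, \text{ if African American".
- **Children (Schwartz bedside).** The conventional version is "0.413 \times \text{height [cm]})/SCr \text{ (mg/dL" and the SI version is "36.2 \times \text{height [cm]})/SCr \text{ (\mu mol/L". There is no sex or race factor. Protocol 6.3.2 assigns the "Schwartz Bedside Formula for patients < 18 years of age at screening".

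eGFR is used for:
- entry: values below 30 are excluded (Protocol 4.2);
- a secondary endpoint to Month 6 and in the extension periods (Protocol 2);
- the efficacy subgroup "Baseline eGFR", cut at 60 (SAP 7.3);
- eGFR shift tables (SAP 7.2) and adverse event tables by eGFR category (SAP 7.7.1).

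The SAP prints no eGFR formula. Neither document says which unit version is used.

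**The concern.** A formula that decides eligibility and feeds a secondary endpoint should return one number for a given patient. Here two sets of patients do not get one.

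For an adult who meets both conditions, *or* can be read as allowing one factor or as allowing each that applies, and the text does not choose. For a child, the two unit versions are presented as equivalent, but the creatinine conversion used elsewhere in the same appendix shows that they are not.

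At stake are which side of 30 or 60 a patient falls on, her or his reported eGFR level, and the absolute change from baseline. If the reading or the unit version changed between visits, the difference would also appear as a change in renal function.

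**Working it through.** The documents give no worked eGFR value, so there is no figure to reproduce. The check evaluates the formulas as printed. All constants come from Appendix 10.1, and the limits of 30 and 60 come from Protocol 4.2 and SAP 7.3. Ages, heights and creatinine values are illustrations.

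**1. MDRD unit versions.** Age 40, creatinine 1.2 mg/dL, no factor: 67.06 in both versions. They agree exactly, because the SI version divides by 88.4.

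**2. MDRD factors.** Men and women who are not African American, and African American men, each have one value. Only an adult African American woman is undefined. The product of the factors is 0.742 × 1.212 = 0.899.

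| Age 40 | Before factors | 0.742 only | Both | 1.212 only |
|---|---|---|---|---|
| SCr 2.0 mg/dL | 37.19 | 27.6 | 33.4 | 45.1 |
| SCr 1.2 mg/dL | 67.06 | 49.8 | 60.3 | 81.3 |

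- Both against 0.742 only: ratio 1.212, so both is 21.2% higher. Equivalently, 0.742 only is 1 − 1/1.212 = 17.5% lower.
- 1.212 only against 0.742 only: 1.212/0.742 = 1.633.

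Comparing 0.742 only with both factors, she changes side when the value before factors lies in these bands:
- limit 30: 30/0.899 = 33.4 to 30/0.742 = 40.4 (at age 40, creatinine about 1.86 to 2.20 mg/dL);
- cut 60: 60/0.899 = 66.7 to 60/0.742 = 80.9 (at age 40, creatinine about 1.02 to 1.21 mg/dL).

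**3. Effect on change from baseline, one reading used throughout.** Age 40, creatinine falling from 1.2 to 1.0 mg/dL: percent change is +23.42% under every reading, because the factor cancels. Absolute change is +11.65 (0.742 only), +14.12 (both) or +19.03 (1.212 only).

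**4. Schwartz unit versions.**
- Constant implied by 0.413 and 88.4: 0.413 × 88.4 = 36.51. Printed: 36.2.
- 36.2/36.5092 − 1 = −0.85%, the same for every child.
- Limit 30: 30 × 36.5092/36.2 = 30.26, so only conventional-unit values of 30.00 to 30.26 change side. Example: 140 cm, 1.92 mg/dL gives 30.11 conventional and 29.86 SI.
- Cut 60: 60 × 36.5092/36.2 = 60.51, so only values just above 60 up to 60.51 change side. Example: 160 cm, 1.1 mg/dL gives 60.07 and 59.56.

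**The case against.** The strongest case against is that this is wording and rounding with almost no reach. Most of its parts stand as limits on size.

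- **Few patients.** The adult gap concerns one demographic group, and the documents do not say how many such women will enrol. This stands: the number may be zero.
- **The natural reading.** Each factor has its own multiplication sign and condition, so applying both is a reasonable reading. A reader might infer that the plan's eGFR can be off by 63%. That figure compares 1.212 only with 0.742 only, and needs someone to skip the sex factor for a woman, the least natural reading. The realistic contrast is 21%.
- **Rounding.** 0.41 × 88.4 = 36.24, so 36.2 fits a coefficient rounded to two decimals. That explains the gap but leaves the two printed versions unequal.
- **SI units.** A reader might infer that the lower SI version is the one in use, because SAP 7.7.2 says "Clinical laboratory parameters will be expressed in Standard International (SI) units". The same paragraph moves eGFR to the efficacy section, and eGFR has the same unit under both versions. The documents do not show which version is used.
- **Central calculation.** Protocol 6.5.6 (Table 8) lists creatinine and eGFR among the central laboratory's tests. One consistent calculation is therefore likely, and nothing shows mixed readings. But the documents do not say what that calculation is.
- **Descriptive endpoint.** SAP 7.2 and its Table 2 footnote exclude eGFR from formal testing. The subgroup result also becomes descriptive if either arm has fewer than 5 patients (SAP 7.3). This stands.

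What survives is that the printed definition is not unique, and the SAP does not resolve it.

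**Conclusion.** The point holds in a narrow form and is minor. Appendix 10.1 gives no defined value for an adult African American woman, with a realistic gap of 21% between both factors and 0.742 only, enough to change eligibility at 30 or the subgroup at 60 within the bands above. Separately, every child's value differs by 0.85% between the two unit versions, which matters for category only in two very thin bands.

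A reader might infer from the list of uses that the eGFR endpoint, entry limit and subgroups depend on the reading for patients in general. They do not: the MDRD unit versions agree, and *or* does not touch men, children or other women. No tested conclusion changes, and percent change is unaffected if one reading is used throughout. Entry, eGFR categories, levels and absolute changes can be affected.

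This rests on the formulas as printed. It assumes nothing about which reading the central laboratory uses or how many affected patients enrol. The bands cover only 30 and 60, because the SAP does not give cut points for its other eGFR categories.

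**What to change.** 1. In both unit versions of the adult formula, replace *or* with an instruction to multiply by each factor that applies, after checking this against the cited source formula. The documents alone do not settle which reading the source intends.
2. For children, name one unit version for all patients and visits, or make the two constants agree (0.413 with 88.4 implies 36.51).
3. Have the SAP cite the corrected appendix as the eGFR definition for the endpoint, the subgroups and the shift tables.
4. Confirm that the central laboratory's calculation matches.

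The cost is two line edits, one SAP cross-reference and one query to the laboratory. Values already calculated can be recomputed from stored creatinine, height, age, sex and race. No new data are needed.
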